234 Liraglutide. The randomized, double-blind, placebo-controlled study design will allow for
235 an independent and unbiased effect of Liraglutide on study results. In addition, actions to
236 equalize weight loss and maintain similar glucose control between study arms will rule out
237 the confounding effects of these factors on the study outcomes.

238 **Specific Objectives**

239 **Primary Objective:**

240 • to test the hypothesis that liraglutide can reduce the pro-inflammatory
241 transcriptome profile of EAT of subjects with T2DM and CAD.

242 **Secondary Objectives:**

243 • to assess the hypothesis that liraglutide will reduce the ultrasound measured EAT
244 thickness in subjects with T2DM and CAD.
245 • to evaluate the hypothesis that liraglutide can produce more anti-inflammatory
246 effects in the EAT as compared to SAT of subjects with T2DM and CAD.
247 • to test the hypothesis that EAT mRNA and protein expression of GLP-1R will be
248 greater in subjects receiving liraglutide as compared to those continuing their
249 standard therapy

250

251 **Research Design and Methods**

252 **Study Hypotheses**

253 **Hypothesis for Primary Objective:** We hypothesize that EAT inflammatory gene mRNA
254 and protein expression will be lower in subjects receiving additional therapy with
255 liraglutide as compared to those who will continue with their current treatment.

256 **Hypothesis for Second Objectives:** based on our biomolecular and clinical preliminary
257 data, we hypothesize that a) EAT thickness will respond and decrease more on liraglutide
258 than on standard therapy, b) inflammatory genes and protein expression will be different
259 in EAT vs SAT c) EAT GLP-1R expression will be greater in patients on liraglutide vs
260 those on standard therapy.

261

262 **Endpoints**

263 **Primary Endpoint:**

264 • Change from baseline in EAT inflammation (measured as mRNA and protein
265 expression of TNF- α and IL-6) within a minimum of 3 and up to 12 weeks of treatment

266 **Secondary Endpoints:** Change from baseline within a minimum of 3 and up to 12 weeks of
267 treatment for the following parameters:

- 268 • Ultrasound measured EAT thickness
- 269 • SAT inflammation (measured as mRNA and protein expression of TNF- α and IL-6)
- 270 • EAT GLP-1R (measured as mRNA and protein expression of GLP-1R)

271 **Study Type**

272 This is an Investigator Sponsored Study (ISS).

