572 **Subject Compliance**

573 We estimate that the majority of the participants who will be considered eligible will
574 complete the study. Attrition can be estimated as lower than 10%. In the event that
575 participants are lost to follow-up, the research coordinator will contact with the study
576 participant by telephone. The research coordinator will be trained in effective telephone
577 technique to maximize recruitment success. All groups will receive lifestyle and diabetes
578 education, as part of the standard care, to insure similar glycemic control between arms.
579 Study patients will be advised to monitor their capillary glucose twice daily, fasting in the
580 morning and post-prandially. Glucose profile will be tracked bi-weekly by the research
581 coordinator by email or telephone.

582

583 **Statistical Considerations**

584 POWER ANALYSIS

585 The statistical power (two-sided, $\alpha=0.05$) of the study was calculated to detect statistically
586 and clinically meaningful differences in the primary endpoint between the two study arms.
587 Our preliminary data showed that EAT inflammatory genes, including IL-6 and TNF- α are
588 upregulated in subjects with T2DM and CAD and higher in EAT as compared to SAT⁴⁻¹⁷.
589 From our recently published study, we calculated the average coefficient of variance (CV)
590 for differential inflammatory genes to be 42%, but for only 5 T2DM patients.¹⁷ As there
591 are no data on the effects of liraglutide on EAT inflammation, the power analysis was based
592 on our previous data and on the assumption that the difference in EAT TNF- α and IL-6
593 expression between liraglutide treated and placebo treated patients would be clinically
594 meaningful at 33% (approx. 1.3X fold). Based on these data, we propose to sample 40
595 individuals. There will be 20 on liraglutide plus standard therapy versus 20 subjects on
596 liraglutide-matching placebo plus standard therapy contributing EAT and SAT samples
597 collected during cardiac surgery. Using the power set at 90% and $\alpha=0.05$, and given the
598 CV of 42%, this sample size will provide adequate power to detect the clinically significant
599 expected difference (33%) in EAT TNF- α and IL-6 between the two study arms.

600 Based on pre-existing data, this sample size will provide adequate power to detect
601 statistically significant differences in EAT TNF- α and IL-6 between the two study arms in

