602 those patients who will receive treatment only for 3 weeks. The difference in EAT TNF- α
603 and IL-6 between liraglutide treated and placebo treated patients is expected to be
604 approximately 1X fold after 3 weeks of treatment.

605

606 The larger sample proposed in this current project would likely reduce the variability. To
607 further assure consistency of results, mRNA and protein expression values will be log-

608 transformed prior to statistical analyses unless they will be normally distributed.
 609 Housekeeping genes will be also used for both RT-PCR and western blot analyses.
 610 In those patients who will not complete the 12-week treatment, the analysis of EAT genes
 611 from the samples will be time adjusted

612
 613 Statistical power was also calculated to detect statistically significant differences in the
 614 ultrasound measured EAT thickness, secondary endpoint, between the two study arms Our
 615 group very recently showed that additional therapy with liraglutide for 12 weeks caused a
 616 reduction in ultrasound measured EAT from 9.6 ± 2 to 6.2 ± 1.5 mm ($p < 0.001$) in 54 patients
 617 with T2DM ¹¹. Given the reference value and the expected difference in EAT, the
 618 statistical power of the study (two-sided, $\alpha = 0.05$) was calculated.

619

Outcome	Reference value \pm SD	Expected Difference	Detectable difference with 80% power $\alpha = 0.05$	Detectable difference with >99% power $\alpha = 0.05$
EAT (mm)	9.6 ± 2	-20-or -30%	-20% (absolute difference = 1.9)	-30% (absolute difference = 2.88)

620

621 Assuming a difference of approximately 2 mm (20%) in EAT to be clinically significant
 622 (based on our recent and previously published data ¹⁰⁻¹⁴), a convenience sample of 20
 623 individuals for each group will therefore provide at least the statistical power (80%) to
 624 detect an expected difference of at least -20% in the EAT before and after treatment with
 625 liraglutide. Baseline standard Deviation (SDs) of 2 is expected to lower to approximately
 626 1.5 for the expected change. The expected change of SD will further assure significant
 627 statistical power of the comparative test.

628

629 In those study patients who will not be able to complete the 12-week treatment, we
 630 anticipate to see a 15% of EAT reduction after 3 weeks in patients who will be allocated to
 631 liraglutide. This anticipated 15% of EAT reduction will remain clinically significant. For

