 632 example, a EAT thickness of 10 mm may likely decrease to 8.5 mm after 3 weeks of
 633 treatment with liraglutide, a clinically meaningful change for the patient cardio-metabolic
 634 profile.

635

636 This sample size also considers the difficulties with recruitment in the real world clinics.
 637 Based on our previous studies in humans, some participants may be lost to follow-up.

638

639 Student's t-test or non-parametric (Mann-Whitney) tests, depending on whether the genes
 640 mRNA expression and protein present or not a normal distribution, will be used to compare
 641 the effects of treatment (liraglutide versus placebo) on the variables measured. Student's
 642 t-test will be also used to compare ultrasound measured EAT thickness before and after
 643 treatments. Continuous variables will be considered as age-adjusted, sex-adjusted and
 644 weight-adjusted means with their SDs or median, if values are skewed.

645 Univariate regression models will be performed to assess the correlation between clinical
646 variables, including echocardiographic EAT thickness and blood tests, and EAT gene and
647 protein expression. Two-tailed $p < 0.05$ indicates statistical significance.

648

649 **Data Handling and Record Keeping**

650 Each of the dedicated clinic exam rooms provides direct access to the clinical research
651 study electronic data capture (EDC) eVelos system provided by the Clinical Research
652 Informatics and Data Management Unit of the Center for Health Informatics and
653 Bioinformatics at University of Miami (UM). The investigator and research coordinator
654 will collect and manage the data.

655 Data collection records with personal identifiers will be stored in locked file cabinets, at
656 [name]. Blood samples drawn
657 and stored in conjunction with this study will not be labeled with information that could
658 directly identify study subjects. Presentation of the study results at scientific meetings or
659 in publications will not identify subjects. Access to research and confidential records will
660 be limited to clinical investigators, research coordinators, and the IRB at UM.

661 **Adipose tissue samples storing**

662 Each adipose tissue sample will be snap frozen in liquid nitrogen and stored at -80°C until
663 analysis in a freezer, in [name] lab, University of Miami, Dept of Microbiology, 1600

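### Four primary measures and no success rule: the stated 5% error and 90% power belong to no defined test of the primary hypothesis

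*Combined protocol and SAP*

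**What the plan says.** All references are to the combined protocol and SAP.

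- **Endpoints, Primary Endpoint:** "Change from baseline in EAT inflammation (measured as mRNA and protein" expression of TNF-alpha and IL-6). Two markers by two assays make four measures.
- **Specific Objectives, Primary Objective:** this is narrower. It speaks of the pro-inflammatory "transcriptome profile of EAT of subjects with T2DM and CAD", which is mRNA only.
- **Study Hypotheses:** this is wider again: inflammatory gene mRNA "and protein expression will be lower in subjects receiving additional therapy with" liraglutide.
- **Statistical Considerations, Power Analysis:** power was calculated, two-sided at 0.05, to detect statistically "and clinically meaningful differences in the primary endpoint between the two study arms". It gives 90% power for a 33% difference (also printed as about 1.3-fold) with 20 per arm. The single CV of 42% is an average over inflammatory genes from five patients. The text does not say mRNA or protein, or either or both. Expression values will be log-"transformed prior to statistical analyses unless they will be normally distributed".
- **Statistical Considerations, analysis paragraphs:** a t-test or Mann-Whitney test compares the arms on each variable measured. The threshold is "Two-tailed $p < 0.05$ indicates statistical significance". That sentence closes the regression paragraph, but it is the only threshold in the analysis text and agrees with the alpha in Power Analysis.

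No section names a lead measure, a composite, an any-or-all rule, a testing order or an adjustment.

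**The concern.** With four tests and no rule, the standard for success can be settled after the results are known. A mixed result, such as IL-6 mRNA significant and TNF-alpha protein not, is realistic, and the plan does not say whether it would support the primary hypothesis. The two natural rules pull in opposite directions: accepting any one measure inflates the false-positive rate, and requiring all four lowers the power. The 5% and the 90% cannot both be read as properties of the trial's primary claim until the rule is known.

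**Working it through.** **Inputs from the plan.** 20 per arm; two-sided 0.05; 33% difference or about 1.3-fold; CV 42%; attrition below 10% (Subject Compliance); no replacement (Subject Replacement).

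**Assumptions.** The plan gives no correlation between the measures and no variability for protein. The joint figures therefore assume a common correlation of 0 to 0.9, the gene CV and the same effect for all four measures, and no dropout. They come from simulated t-tests and are good to about one percentage point.

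**1. The stated 90% for one test.** Exact two-sample t power uses 38 degrees of freedom and noncentrality d × √(20/2). On the log scale the SD is √ln(1 + 0.42²) = 0.403. Power of 90% needs d = 1.052. At correlation 0, all-four power is the single-test power to the fourth power, for example 0.8118⁴ = 0.434.

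| Reading of the inputs | d | One test | All four (correlation 0 to 0.9) |
|---|---|---|---|
| Log scale, 33% reduction (ratio 0.67, i.e. 1/0.67 = 1.49-fold) | 0.400/0.403 = 0.994 | 86.5% | 56–79% |
| Raw scale, CV 42% in both arms | 0.33/[0.42√((1 + 0.67²)/2)] = 0.923 | 81% | 43–72% |
| Raw scale, common SD | 0.33/0.42 = 0.786 | 67.8% | 21–55% |
| Log scale, 1.33-fold | 0.285/0.403 = 0.708 | 58.7% | 12–45% |
| Log scale, printed 1.3-fold | 0.262/0.403 = 0.651 | 51.8% | 7–38% |

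None gives 90%. The closest is the first row, which a normal approximation puts at 88.1%. Values above 90% appear only on departing from the planned test: for example, 92.5% for a one-sided t-test on the first row, or 91.5% for a one-sample t-test with d = 0.786.

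**2. Any one of four suffices.** With independent measures the false-positive rate is 1 − 0.95⁴ = 18.5%. At correlation 0.5, 0.8 and 0.9 it is about 15.6%, 11.5% and 9.5%. If only reductions count, it is at most 1 − 0.975⁴ = 9.6%, falling to about 5%, against a nominal 2.5%. With only the two mRNA measures it is at most 1 − 0.95² = 9.75%, falling to about 7%.

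**3. All four required.** The false-positive rate is at most 5%. From a true 90% per test, joint power is 0.9⁴ = 66% at correlation 0, then about 74%, 80% and 83% at 0.5, 0.8 and 0.9.

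**4. Chance of a mixed result.** If all four effects are real and equal, the chance that some but not all reach p < 0.05 is about 14–44% on the first row of the table and 24–78% on the third.

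**5. Attrition.** At 18 per arm (10% loss), single-test power is 82.5% on the first row and 62.9% on the third.

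**The case against.** The best defence is that the hypothesis is worded conjunctively: mRNA and protein, TNF-alpha and IL-6. Read as an all-four requirement, the 5% error is controlled without adjustment. That is the reading closest to the text. But nothing states it as the criterion for success, and 90% would not be its power.

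A second defence is that the objective makes mRNA the lead. That would explain the gene-based CV, but it still leaves two genes and no rule.

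Third, markers from one biopsy are likely to be correlated. This stands: 18.5% is a ceiling reached only at zero correlation. At 0.9 the rate is still about 9.5%.

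Fourth, this is a 40-patient mechanistic study which Regulatory Considerations says is not meant to support labelling. This also stands and limits the weight of the point. Even so, a plan that states a primary hypothesis, an alpha and a power should say which result supports that hypothesis.

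A reader might infer that the plan specifies no test at all. It does not go that far: a test and a threshold are given for each variable. What is missing is the step from four results to one conclusion.

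**Conclusion.** The point holds. The plan has four primary measures, each tested at two-sided 0.05, and no rule linking them to the primary hypothesis. The resulting error rate is at most 5% if all four must succeed and about 9.5% to 18.5% if any one is enough. Joint power under the all-four rule is about 66% to 83% from a true 90% per test, and lower on every reading of the plan's own inputs. The 90% is not reached for a single two-sided, two-sample t-test on any of the five readings tried (51.8% to 86.5%).

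The joint figures rest on assumed correlations and on applying the gene CV and a common effect to the protein measures. The absence of a rule rests on the text alone.

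Two stronger conclusions are tempting and not supported. One is that the trial runs at an 18.5% error rate: that needs both an any-one rule and independence, and the documents state neither. The other is that 20 per arm has been shown to be too few: that depends on the rule, the scale and the fold change, which the plan leaves open.

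The sponsor should correct this, but it does not invalidate the trial.

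**What to change.** Before treatment codes are linked to assay results, state one success rule in Statistical Considerations. Any of these would do:

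- **Lead measure with fixed order.** Name one EAT mRNA measure and test it at two-sided 0.05. Test the other three in a listed order at 0.05, each only if the previous one is significant. An mRNA lead matches the objective and the gene-based CV. The investigator chooses the gene; the order in which the documents list the two genes does not settle it.
- **All four required**, stated explicitly. This is closest to the wording of the hypothesis.
- **Holm across the four.**

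For the chosen rule, fix the test and the scale for each measure. Replace the 90% with the power of that rule, giving the fold change, CV, scale and attrition used.

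The cost is wording, with no extra patients or assays, but the stated power will look less favourable. The figures below use the first and third rows of the table, in that order, with equal real effects:

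- **Fixed order:** the lead keeps 86.5% or 67.8%. A later measure cannot be claimed once an earlier one fails, and the chance of claiming the second is about 75–83% or 46–61%.
- **Holm:** power per measure is about 77–82% or 53–54%.
- **All four:** joint power is 56–79% or 21–55%.

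Study Schedule plans the last visit for 10/31/2023. If codes are already linked, report all four estimates with confidence intervals and p-values, and label any success rule as post hoc.

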273 This will be a 12-week randomized, double-blind, placebo-controlled interventional study
274 in 40 patients with T2DM and CAD with an acceptable glycemic control on their current
275 diabetes regimen who require elective coronary artery bypass grafting (CABG) regardless
276 of their participation in the study.

277 A minimum time frame of 3-week treatment will be considered to detect significant
278 changes in the study endpoints. If not all subjects would be able to complete the 12
279 weeks, study outcomes will be evaluated at the 3 week time point.

280

281 **Study Design** Study subjects will be randomized in two groups of 20 patients to receive
282 additional liraglutide, (L-group) or to remain on current treatment or placebo (D-group).

- 283 • L-group will be started on liraglutide. Liraglutide will be started and administered
284 for 12 weeks prior to CABG with a starting dose of 0.6 mg (after a least one week)
285 and subsequent increments to 1.2 mg (after a least one week) and to 1.8 mg (after
286 at least a week on 1.2 mg). The dose of 1.8 mg daily will be maintained until the
287 end of the 12-week study. Other and current diabetes treatment will be continued.
288 In those study participants who may be impacted by CABG scheduling and
289 COVID-19, and cannot complete the 12-week treatment, we will consider a
290 minimum time frame of 3 weeks to detect significant changes in the study primary
291 endpoints.
- 292 • D-group: placebo will be administered in addition to current treatment prior to the
293 CABG with a starting dose of 0.6 mg (after a least one week) and subsequent
294 increments to 1.2 mg (after a least one week) and to 1.8 mg (after at least a week
295 on 1.2 mg). Patients will be started on a supervised diet to achieve approximately
296 5% of weight loss between 3 and 12 weeks. In those study participants who may be
297 impacted by CABG scheduling and COVID-19, and cannot complete the 12-week
298 treatment, we will consider a minimum time frame of 3 weeks to detect significant
299 changes in the study primary endpoints.

300

301 Ultrasonographic measurement of EAT thickness will be performed at baseline and
302 after 12 weeks in all patients, regardless of the study arm.

303 All groups will receive lifestyle and diabetes education, and supervised diet as
304 part of the standard care, to insure similar glycemic control between arms and
305 weight loss. Study patient will be also required to check and log their finger stick

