307 blood glucose twice daily (fasting before breakfast and at bedtime) and report the
308 readings to the study coordinator on a bi-weekly base.
309

310 **Rationale for study Design**

311 The randomized, double-blind, placebo-controlled study design will allow for an
312 independent and unbiased effect of liraglutide on study results.
313

314

315 **Rationale for minimum study time line of 3 weeks.**

316 The pre-operative clinic schedule may not always allow to wait the full 12 weeks between
317 the patient's enrollment and the CABG, standard of care procedure. [name] is the only
318 cardiac surgeon at UM performing elective CABGs. Once the patient is randomized and
319 randomly allocated to one of the study arms, the length of the treatment is set by the date
320 of standard of care CABGs. During the current COVID-19 pandemic, the number of
321 elective CABGs has been reduced and we cannot reschedule or delay the surgery
322

323 **Study Population:** Study group will be formed by 40 patients with T2DM and with
324 clinically and angiographically stable CAD who will undergo CABG surgery, as part of
325 their standard medical care. Cardiac surgery will be elective procedure in
326 hemodynamically stable patients taking their standard cardiac treatments and under the
327 care of the cardiologist.

328

329 **Study team and site:** [name] is Professor of Medicine, Division of
330 Endocrinology, Diabetes and Metabolism. [name] pioneered EAT echocardiographic
331 measurement and he is considered the leading expert in the epicardial fat. [name] will
332 lead and supervise liraglutide therapy, EAT measurement, analysis and interpretation of
333 the data. [name], Research Assistant Professor, Dept. Microbiology and Immunology,
334 will lead and supervise adipose tissue analysis. [name] is associate professor
335 of Cardiology and contributes to patient recruitment. [name], professor of
336 cardiothoracic surgery will be the cardiac surgeons for this study. Low calorie diet (LCD)
337 and other nutritional aspects will be managed and supervised by the Division of
338 Endocrinology registered dietitian (RD), as part of the standard care. University of Miami
339 has been the site of several National Health Institute (NIH) studies and many peer-reviewed
340 publications. The Division of Endocrinology Diabetes and Metabolism is fully equipped
341 and trained to visit, follow up and manage patients with diabetes. The Division of

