480 correlation coefficient. Inter- and intra-observer reproducibility will be evaluated by the
481 intra- class correlation coefficient in all subjects. Echocardiograms will be read by Dr
482 [name] and an experienced cardiac imaging technician. Previously published studies
483 have shown that intra- and inter-observer reproducibility of epicardial fat measurement was
484 excellent. Intra-class correlation coefficients varied from 0.90 to 0.98 and from 0.93 to
485 0.98, respectively indicating good reproducibility and reliability. Both readers will be
486 blinded to the subjects' clinical data.

487 **Anthropometrics and Clinical measures:** As standard of care, height (in cm) and weight
488 (in kg) will be measured, and BMI will be calculated. Waist circumference (in cm or
489 inches) will be measured as the minimum circumference between the lower rib margin and
490 the iliac crest. Blood pressure will be also measured.

491 **Blood Measurements:** Lipid panel, lipase, and amylase are not study end-points and will
492 be collected if made available through a standard of care procedure at baseline and after 4
493 or 12 weeks.

494 **Low calorie Diet (LCD)** A low calorie diet program will be prescribed to study patients
495 and controls. A RD who will reach out to patients to insure adherence to the dietary
496 program will supervise the LCD. This will help patients to achieve approximately 5% of
497 weight loss between 3 and 12 weeks.

498 **Assessments for Safety**

499 **Potential Risks to the Subjects**

500 The risks of this study are minimal are mainly related to risks associated with the
501 investigational drug liraglutide, echocardiogram, blood draw, and a potential breach of
502 confidentiality.

503 **Drug therapy:** liraglutide, (Victoza®), is a GLP-1A indicated as an adjunct to diet and
504 exercise to improve glycemic control in adults with T2DM. Liraglutide is taken once daily
505 at any time of day, without regard to the timing of meals. Liraglutide is injected

506 subcutaneously in the abdomen, thigh, or upper arm. Liraglutide may cause mild and
507 usually well-tolerable gastro-intestinal side effects (5%), such as nausea, constipation.
508 Liraglutide is contraindicated in patients with a personal or family history of medullary
509 thyroid cancer and in patients with Multiple Endocrine Neoplasia (MEN). Based on
510 spontaneous postmarketing reports, acute pancreatitis has been observed in patients treated

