702 evaluate the temperature. Prior to first use, trial drugs will be stored in a refrigerator
703 between 36°F to 46°F (2°C to 8°C). After initial use of the trial drug pen, the pen can be
704 stored for 30 days at controlled room temperature (59°F to 86°F; 15°C to 30°C) or in a
705 refrigerator (36°F to 46°F; 2°C to 8°C). Trial drugs will be not dispensed to any person not
706 enrolled in the study. Unused trial drugs will be stored separately from used trial
707 medication.

708 **Randomization and Blinding**

709 This will be a double-blind, parallel group, placebo controlled study. The method of
710 allocation generation will be a computerized random-number generator. The sequence will
711 be generated by the process of restricted randomization. Computer-based randomization
712 process will be managed by the UM Research pharmacy.

713

714 **Concomitant Illnesses and Medications**

715 **Background medications:**

716 **Metformin.** Metformin is considered background medication (non-investigational
717 medicinal product) and will not be provided during the trial. Dose adjustments could occur
718 during the trial at the investigator’s discretion. As [name] et al ¹² recently showed no
719 significant effects of metformin on EAT, we do not anticipate that metformin dose
720 adjustment may influence the study outcomes.

721 **Long acting insulins.** Insulin is considered background medication (non-investigational
722 medicinal product) and will not be provided during the trial. The total daily dose of insulin
723 could be adjusted during the trial at the investigator’s discretion. [name]’ group recently
724 performed a 24-week interventional study to compare EAT changes in insulin-naïve

725 inadequately controlled patients with type 2 diabetes following basal insulin initiation with
726 detemir vs. glargine. No significant changes in EAT between detemir and glargine were
727 observed. ²¹ Based on these findings we do not anticipate that insulin treatment may
728 influence the study outcomes.

729 **Sulfonylureas.** Sulfonylurea treatment is considered background medication (non-
730 investigational medicinal product) and will not be provided during the trial. During the
731 study, no up-titration of sulfonylurea dosage will be allowed. Dose reduction of SU due to
732 hypoglycemia may be allowed at the investigators discretion. In the event of
733 hypoglycemia, the dose of sulfonylurea can be reduced or the drug can be stopped at the

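### Similar glucose control is said to remove glycaemic confounding, but the design does not secure it, no analysis checks it, and the reassurance about insulin rests on a comparison of two insulins

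*Combined protocol and SAP*

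**What the plan says.** **The claim.** Study Rationale states that actions to "equalize weight loss and maintain similar glucose control between study arms will rule out" the confounding effects of weight and glucose on the outcomes.

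**The means.** Study Design ties similar glycaemic control to education and diet: "All groups will receive lifestyle and diabetes education, and supervised diet as" part of standard care. Subject Compliance repeats education for this purpose.

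**Background drugs.** Under Concomitant Illnesses and Medications, metformin and long-acting insulin may be adjusted as the investigator judges, with no target or algorithm. For sulfonylureas, during the "study, no up-titration of sulfonylurea dosage will be allowed"; reductions are permitted.

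**Why insulin is set aside.** The same section describes a 24-week study in insulin-naïve patients starting "detemir vs. glargine. No significant changes in EAT between detemir and glargine were" observed. It continues: "Based on these findings we do not anticipate that insulin treatment may" influence the study outcomes.

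**Glucose data.** Study Design asks patients to log "blood glucose twice daily (fasting before breakfast and at bedtime) and report the" readings every two weeks. Subject Compliance asks for a fasting reading in the "morning and post-prandially. Glucose profile will be tracked bi-weekly by the research" coordinator. HbA1c appears only as an eligibility limit (at most 9%). Blood Measurements says "Lipid panel, lipase, and amylase are not study end-points and will" be collected only if standard care provides them. Study Timetable plans a laboratory draw at baseline and before surgery without listing its contents.

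**Analysis.** Statistical Considerations names age, sex and weight as adjustment variables, and univariate regressions of expression on clinical variables and blood tests.

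**The concern.** The protocol itself describes liraglutide's glucose-lowering effect as well established (Cardiovascular effects of Liraglutide). If both arms receive the same education and diet, and only one receives the drug, nothing in the stated plan makes glucose similar. If it does turn out similar, something else, such as background doses or adherence to diet, may have differed between arms. No planned table or test would show which of these happened.

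What is at stake is interpretation. Short term effects of Liraglutide on inflammation argues that a direct effect on the epicardial fat transcriptome is more likely than one mediated by weight loss or glycaemic control. Study Rationale then treats glucose as excluded. Followed as written, the trial could report a glucose-independent effect that neither its design nor its analysis supports.

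**Working it through.** The protocol gives no figure for this claim, so there is none to reproduce. The first three steps are checks of logic and of data collection. The fourth asks what a glucose comparison could show.

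**1. Does the design make glucose similar?**
- Liraglutide arm: drug, education, diet, adjustable insulin and metformin.
- Placebo arm: placebo, education, diet, adjustable insulin and metformin.
- The planned difference is a drug that lowers glucose. Study Design states a diet goal of about 5% weight loss in the placebo bullet, but the Low calorie Diet section gives the same goal to study patients and controls. Diet is therefore not a clear counterweight in one arm.

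**2. Does the detemir–glargine result support the inference about insulin?**
- Let *a* be the effect of starting detemir on EAT and *b* the effect of starting glargine. The study compares them, so it informs *a* − *b*.
- A difference near zero fits *a* = *b* = 0, and equally *a* = *b* = any other value. As described, there is no arm without insulin and no contrast of doses.
- The quantity needed here is the effect of more versus less insulin on TNF-α and IL-6 mRNA and protein. The comparison, as described, addresses neither that contrast nor that outcome.
- The citation does not match either. Superscript 21 leads to a study of preadipocytes, while the detemir–glargine study is listed as reference 14. Likewise, the metformin reassurance cites reference 12, whose listed title concerns GLP-1 receptor agonists. The documents do not show what it found on metformin.

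**3. Is a check planned?**

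| Item | Collected | Between-arm analysis planned |
|---|---|---|
| Finger-stick glucose | Yes, twice daily; second reading defined two ways | No |
| HbA1c on treatment | Not specified | No |
| Insulin, metformin, sulfonylurea dose | No dose summary specified | No |
| Pre-surgery blood draw | Yes, contents not specified | No |

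Both versions of the log contain a fasting reading, so fasting values can be compared between arms despite the inconsistency.

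**4. What could such a comparison show?**
Inputs: 20 per arm (Power Analysis); attrition below 10% (Subject Compliance), taken at its limit as 18 per arm. The 95% interval half-width for a difference in means, in SD units, is t(0.975, 2n − 2) × √(2/n).
- n = 20: 2.024 × √(2/20) = 2.024 × 0.316 = 0.64 SD.
- n = 18: 2.032 × √(2/18) = 2.032 × 0.333 = 0.68 SD.
- Difference detectable with 80% power at n = 20 (normal approximation): (1.960 + 0.842) × 0.316 = 0.89 SD.

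Arms that truly differed by half an SD would often give a non-significant result, so non-significance would not establish similarity.

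**The case against.** The best defence is that the primary objective, hypothesis and endpoint ask whether expression is lower on liraglutide than on placebo, and none of them requires glucose independence. The wording on insulin is an expectation, not a guarantee. The direct-effect argument also leans on GLP-1 receptor expression in EAT, and Preliminary Data reports that EAT shrank independently of weight loss and glucose control. Entry limits (HbA1c at most 9%, acceptable control on the current regimen, exclusion of several drug classes) restrict how far background therapy can diverge. All of this stands. It confines the problem to interpretation, but it does not rescue the Study Rationale claim: the earlier result concerned thickness, not gene expression, and entry limits do not equalise glucose on treatment.

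Three stronger readings are tempting, and the documents do not support them.
- **That glucose is to be equalised by changing insulin and metformin.** The stated means are education and diet. Dose changes are permitted, with no equalising purpose given.
- **That glycaemic similarity cannot be checked.** Finger-stick readings are logged and tracked every two weeks. What is missing is a planned analysis.
- **That the primary comparison is biased by a calculable amount.** Glucose and dose changes arise after randomisation, so they are mediators or intercurrent events rather than baseline confounders. The documents give no effect of glucose or insulin on expression, and a background-therapy effect could either widen or narrow the contrast.

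**Conclusion.** The point holds in a limited form. The statement that glucose confounding is excluded is not supported by the stated means, the planned data or the planned analysis, and the insulin inference does not follow from the study described. The randomised, blinded comparison of liraglutide with placebo, each added to background therapy, remains valid. Attribution of any difference to a direct, glucose-independent action is what lacks support.

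No size can be given for a glucose or insulin effect on TNF-α or IL-6 expression. The only figure that can be derived is the precision of a check: about ±0.64 SD at 20 per arm and ±0.68 SD at 18, assuming roughly normal values and equal variances. The conclusion takes the protocol's description of liraglutide as glucose-lowering, and its description of the two-insulin study, at face value.

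**What to change.** - In Study Rationale, delete the assertion that confounding by glucose is excluded. Under Long acting insulins, delete the inference from detemir versus glargine. Correct the reference numbers.
- Define the primary contrast as the effect of adding liraglutide to adjustable background therapy.
- Record insulin, metformin and sulfonylurea doses at baseline, at the existing bi-weekly contacts and at the pre-surgery visit.
- Report fasting finger-stick glucose and background doses by arm beside the primary result, as differences with 95% confidence intervals. Do not read similarity from a non-significant difference.
- Specify HbA1c and fasting glucose at baseline and before surgery, where blood is already to be drawn. Note that HbA1c responds slowly, so it will say little after a 3-week exposure.
- Present any statement on glucose independence as exploratory. Similar glucose with different insulin doses would still leave an insulin effect possible.
- Reconcile the two self-monitoring schedules (Study Design and Subject Compliance). The investigator should also reconcile the background-medication rules with the aim of similar glycaemic control; how to do so is a clinical matter.

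The cost is protocol wording, a dose field at contacts that already take place, and minor assay work. The price is a more modest mechanistic claim. Nothing here needs a change to the randomised treatments or the sample size.
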